27.2 Analysis of secondary outcomes

- Back pain intensity will be analyzed using the same model used to analyze the primary outcome.
- Disability and sciatica bothersomeness will be analyzed using the same model used to analyze the primary outcome, but with 3 time points.
- Responder analyses, i.e. 30% and 50% improvement in leg pain intensity, will be performed using a mixed effects logistic regression model to obtain estimates of odds ratios (OR) and 95% CI. Based on the absolute risk reduction (ARR) between Naproxen and placebo we will calculate the numbers needed to treat (NNT) with 95% CI (NNT = 1/ARR).
- Rescue medication consumption and concomitant use of opioids during the treatment period will be analyzed using a suitable regression.
- Work/Study is an unordered categorical variable. The appropriate model is therefore a multinomial with repeated measurements and it will be analyzed using a GLMM.
- Global perceived change is an ordered categorical variable with repeated measurements and will be analyzed using a GLMM.

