### 2.4 SECONDARY ENDPOINTS

- The change in back pain (24 hours average) rated on a 0-10 numeric rating scale (NRS) from baseline to day 10 based on longitudinal analyses of daily observations.
- The change in disability assessed by the Roland Morris Disability Questionnaire for sciatica (RMDQ-S) based on longitudinal analyses of observations at baseline, day 5 and day 10.
- The use of rescue medication, i.e. number of Paracetamol tablets taken between baseline and day 10.
- The number of patients who at day 5 and day 10 report their pain to be *completely gone, much better and better* on a Global Perceived Change (GPC) scale
- The change in sciatica symptoms assessed by the Sciatica Bothersomeness Index (SBI) based on longitudinal analyses of observations at baseline, day 5 and day 10.
- The number of patients who at day 5 and day 10 have a (i)  $\geq 30\%$  and a (ii)  $\geq 50\%$  reduction in leg pain score relative to baseline
- The use of (i) weak opioids and (ii) strong opioids assessed by the number of Defined Daily Doses (DDD) between baseline and day 10
- The number of patients who at day 10 are able to work/study as normal

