## 9.5 STATISTICAL ANALYSIS

### 9.5.1 Statistical methodology

The primary analyses will be performed by linear mixed effects models for repeated measures (MMRM) [88]. Mean changes from baseline will be analyzed using a restricted maximum likelihood (REML) based repeated measures approach. Analyses will include the categorical effects of treatment and treatment-by-visit interaction as fixed covariates and intercept as a random variable. Additionally, responder analyses comparing the percentage of patients who have

improved according to predefined cut-offs in the two groups (see 2.2), will be performed using a  $\chi^2$  test [89]. The strategy for dealing with missing values will be decided during the blind review of the data at the end of the trial. A statistical analysis plan will be prepared and made accessible at clinicaltrials.gov.

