26.2 Calculations of outcomes

- The RMDQ-S is scored by summing up the number of items the patient checks.
- The SBI consists of four sciatica symptoms. Each symptom is rated 0-6 and a total bothersomeness score is obtained by summing up the ratings across the four symptoms
- The responder outcomes will be calculated as the change in leg pain scores between baseline and end of treatment, relative to baseline. Subjects with $\geq 30\%$ reduction in leg pain intensity will be classified as a 30% responder, others as non-responders. A similar procedure will be used to identify 50% responders.
- Use of weak opioids will be quantified using a weighted score by dividing the total dose taken from day 0 to day 10 by its respective DDD. The DDD is the assumed average maintenance dose per day for a drug used for its main indication in adults [3].
- Use of strong opioids will be quantified by the total dose converted into morphine milligram equivalents (MME) [4].

27 Analysis methods

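### The 30% and 50% responder outcomes have one yes/no result per patient in SAP 26.2 but a mixed-effects logistic model in SAP 27.2; time points, random effect and missing-score rule need to be stated and reconciled with the protocol

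*SAP*

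**What the plan says.** - **Definition (SAP 26.2).** "The responder outcomes will be calculated as the change in leg pain scores between baseline and end of treatment, relative to baseline". A patient who reaches the cut-off "will be classified as a 30% responder, others as non-responders"; the 50% outcome is handled in the same way. This gives one yes/no result per patient and cut-off. No rule is given for a missing day-10 score.
- **Model (SAP 27.2).** The responder analyses "will be performed using a mixed effects logistic regression model to obtain estimates of odds ratios (OR) and 95% CI". An NNT with 95% CI is to be calculated from the absolute risk reduction (ARR). The same section mentions repeated measurements for work/study status and for global perceived change, but not for the responder outcomes.
- **Random effects (SAP 27.3).** Centres may enter as further random effects, which implies that the basic one is the patient.
- **Missing data (SAP 28.3).** The missing-at-random statement covers the primary and the continuous secondary outcomes. Multiple imputation is for outcomes that are not analysed by LMM or GLMM.
- **Protocol 2.4.** The endpoint is "The number of patients who at day 5 and day 10 have a" 30% or 50% reduction, so there are two time points.
- **Protocol 9.5.1.** The comparison of patients who "improved according to predefined cut-offs in the two groups (see 2.2), will be performed using a" test that the sentence goes on to name as chi-square.
- **Planned Table 2 (SAP).** One row per cut-off with no day stated, a percentage with 95% CI per arm, and a difference with 95% CI.

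**The concern.** A patient random intercept is estimated from the agreement between repeated results in the same patient. With a single binary result there is no such agreement to observe. The data then cannot separate a small between-patient variance with a modest odds ratio from a large variance with a large one. The reported odds ratio would rest on starting values and approximations in the software.

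The definition and the missing-data section also leave a gap. A binary outcome analysed by GLMM falls under neither sentence of SAP 28.3, and the residual category in SAP 26.2, read literally, takes in patients with no day-10 score. If it were applied that way, unequal dropout would turn into an apparent treatment difference. That would affect the percentages, the ARR and the NNT, which are the results that clinicians are most likely to use.

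**Working it through.** **The plan's own figure.** Inputs from Protocol 9.1: difference 1.5, SD 2.5, two-sided 5%, 90% power. Normal approximation: 2 × (1.960 + 1.282)² × 2.5² / 1.5² = 58.4, so 59 per arm. The noncentral t gives 60 per arm with power 0.903. Then 120 / 0.80 = 150. The sample size reproduces, and this point does not touch it. The documents give no response rates and no missingness by arm, so all rates below are assumptions.

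**One record per patient, treatment arm only.** Take 75 per arm, with expected counts at 35% (placebo) and 50% (naproxen). For each fixed random-intercept SD, solve for the arm intercepts whose averaged probabilities equal 0.35 and 0.50. The log-likelihood is 75 × [0.35 ln 0.35 + 0.65 ln 0.65] + 75 × ln 0.50 = −100.5445. It depends only on those averaged probabilities, so it is the same at every SD. The conditional odds ratio is not:

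| Assumed response | SD 0 | SD 1 | SD 2 | SD 3 |
|---|---|---|---|---|
| 35% vs 50% | 1.86 | 2.11 | 2.76 | 3.82 |
| 40% vs 55% | 1.83 | 2.08 | 2.72 | 3.73 |
| 30% vs 45% | 1.91 | 2.17 | 2.87 | 4.00 |

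The SD 0 column is ordinary logistic regression, for example (0.50/0.50) / (0.35/0.65) = 1.86. In every row the ARR is 15 points and the NNT is 1/0.15 = 6.7, whatever the SD.

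**One record per patient, with covariates.** Continuous covariates identify the variance formally, through the shape of the link. To see how strongly, 40 trials of 150 patients were simulated with baseline pain, age and sex as covariates and a true SD of 2. Over SD 0 to 4 the profile log-likelihood varied by a median of 0.02 and at most 0.09 units; a 95% limit needs a drop of 1.92. The median conditional odds ratio moved from 2.0 to 7.0 over that range.

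**Two records per patient (day 5 and day 10, as in Protocol 2.4).** In the same simulations, fitted with a day effect and a common treatment effect, the median log-likelihood was highest at SD 2. It fell by 8.3 at SD 0, 2.4 at SD 1, 2.7 at SD 3 and 7.1 at SD 4. Here the random effect is identifiable.

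**Missing day-10 score counted as non-response.** If missingness is unrelated to response, the observed rate is the true rate × (1 − proportion missing).

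- 50% in both arms, 10% vs 20% missing: 0.50 × 0.90 = 45% and 0.50 × 0.80 = 40%, a spurious 5 points.
- 40% in both arms, 10% vs 20% missing: 36% and 32%, a spurious 4 points.
- 35% vs 50%, 20% missing in both arms: 28% vs 40%, NNT 8.3 instead of 6.7.
- 35% vs 50%, 20% missing on placebo and 10% on naproxen: 28% vs 45%, NNT 5.9.
- 35% vs 50%, 10% missing on placebo and 20% on naproxen: 31.5% vs 40%, NNT 11.8.

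**NNT when the ARR interval includes zero.** For 50% vs 40% with 75 per arm, SE = √(0.25/75 + 0.24/75) = 0.081. The ARR is 0.10 (−0.06 to 0.26). Inverting the unrounded limits gives about −17 and 3.9. Written as one range, these do not contain the estimate of 10, and the SAP does not say how such a case is presented.

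**The case against.** The best defence is that SAP 27.2 never specifies a patient intercept on a single record. Leg pain is recorded daily, Protocol 2.4 sets two days, and on two days the mixed model is suitable. A centre random effect would also be identifiable in principle. This stands in part: a reader might infer that a mixed logistic model is wrong for these outcomes, and the documents taken together do not support that. The fault may lie in an incomplete definition in SAP 26.2. But the SAP as written, including the single undated rows of Planned Table 2, points to one record.

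A reader might also infer that the SAP imposes failure coding, or contradicts its own missing-at-random assumption. Neither follows. SAP 26.2 calculates a change, and without a day-10 score there is none. SAP 32 shows sample sizes for non-missing values. The missing-at-random sentence does not extend to binary outcomes. This is a gap, not a conflict. Differential missingness of 10% versus 20% is also pessimistic: the plan's 20% is an upper bound on dropout and non-compliance combined, and data collection continues after patients stop only the study drug (Protocol 6.4.1; compare SAP 28.1).

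Nor is the NNT arbitrary or invalid. It does not depend on the random effect, and a disjoint interval for benefit and harm is a legitimate presentation.

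SAP 27.4 allows other models if the data challenge the assumptions. That does not settle a mismatch that is visible before any data are seen.

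**Conclusion.** The point holds in limited form. Followed as written, with the patient as the implied random effect, SAP 26.2 and 27.2 give a conditional odds ratio that the data cannot determine in practice: 1.86 to 3.82 over SD 0 to 3 under assumed response of 35% versus 50%, with similar ranges for neighbouring rates. On the protocol's two time points the problem disappears, so the need is to reconcile the passages; the documents do not show that the model class itself is wrong. The missing-score rule is absent. Its possible effect is a spurious difference of 4 to 5 points, or an NNT between 5.9 and 11.8 instead of 6.7, under assumed missingness of 10% to 20% per arm. These figures illustrate the size and do not predict the trial's result. Only secondary outcomes are affected. The change is worth making, but it does not bear on the primary analysis or the sample size.

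**What to change.** Choose one of two specifications in SAP 26.2 and 27.2:

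- **(a)** Ordinary logistic regression at day 10, and separately at day 5, adjusted for baseline leg pain, age and sex.
- **(b)** Responder status at day 5 and day 10 in a mixed logistic model with a patient random intercept, time and treatment-by-time, with the day-10 contrast named as the result.

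In both cases:

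- Impute the NRS scores first and dichotomise afterwards, and state in SAP 28.3 that this applies to the responder outcomes.
- Define non-responders as patients whose observed or imputed percentage reduction from baseline is less than 30% (or 50%).
- Use the risk difference with 95% CI already foreseen in Planned Table 2 as the basis for the NNT. When its interval includes zero, show the NNT together with the ARR interval.
- Record and justify the departure from the chi-square test in Protocol 9.5.1, and add the day to the responder rows of Planned Table 2.

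The cost is SAP wording and a little programming. SAP 28.3 already plans 50 imputed data sets, and the daily scores are already collected.

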27.3 Adjustment for covariates

The statistical analyses of primary and secondary efficacy outcomes will be adjusted for baseline measures of the outcome where one is available [5]. The analysis of rescue medication consumption and use of concomitant opioids will be adjusted for baseline leg or back pain intensity depending on which is worse.

Study center (stratification variable) will not be included as covariate as we expect the majority of participants to be included at one center (Østfold). We will perform a sensitivity analysis with and without adjusting for center. Provided that a sufficient number of patients are included from at least 4 centers, these can be treated as additional random effects in the model.

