# **9 STATISTICAL METHODS AND DATA ANALYSIS**

## **9.1 DETERMINATION OF SAMPLE SIZE**

The sample size calculation is based on a mean difference between the Naproxen group and the placebo group of 1.5 (0-10) at ten days with a SD of 2.5 using a two-sample t test. There is no robust evidence for the smallest worthwhile

between group pain relieving effect in sciatica. In previous sciatica studies sample size were calculated based on between group differences of 1.5 and 1.0 [80, 81]. In a recent RCT of pregabalin the sample size was calculated based on a between group difference of 1.5 [36]. In knee osteoarthritis, a condition in which NSAIDs are generally recommended, the treatment effect of NSAIDs is about 1.0 [82-84]. The estimated SD of 2,5 is based on a recent Cochrane review of NSAID studies in sciatica [30].

Assuming 90% power and a two-tailed 5% significance level a sample size of 60 subjects is needed in each treatment arm. Allowing for a combined dropout and non-compliance rate  $\leq 20\%$  [85] the total number of subjects will be 150.

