8.2 Secondary objectives

To demonstrate that, in patients with sciatica, treatment with Naproxen 500 mg twice daily is superior to placebo with respect to

- improvement in back pain intensity
- improvement in disability
- use of rescue medication
- global perceived change in sciatica/back problem
- improvement in sciatica symptom bothersomeness
- 30% and 50% improvement in leg pain
- concomitant use of opioid analgesics
- ability to work and study

STUDY METHODS

9 Trial Design

NIS is a multicenter, two-armed randomized, placebo controlled, double blind, parallel group, superiority phase IV trial.

10 Randomization

Study medicines will be packaged and labelled according to a pre-generated random number sequence; each sealed box will have a unique participant number. Computer-generated block randomization, stratified by center, will be used. Allocation to Naproxen or placebo will be at a 1:1 ratio.

11 Sample size

The sample size estimation is based on a minimum difference of interest between the Naproxen group and the placebo group of 1.5 at day 10. Assuming a standard deviation SD of 2.5 (see protocol for details and references), 90% power and a two-tailed 5% significance level, 60 subjects in each treatment arm is required. Allowing for a combined dropout and non-compliance rate $\leq 20\%$ a sample size of 150 was determined.

12 Framework

Analyses will be within a superiority hypothesis testing framework, comparing Naproxen to placebo.

13 Interim analyses and stopping guidance

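### As written, SAP 27.3 leaves global perceived change without baseline adjustment, although baseline pain is collected and already serves as a substitute covariate for rescue and opioid use

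*SAP*

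**What the plan says.** SAP 27.3 sets the general rule: "The statistical analyses of primary and secondary efficacy outcomes will be adjusted for baseline measures of the outcome where one is available". It then makes one provision of a different kind: the analyses of rescue medication and concomitant opioids "will be adjusted for baseline leg or back pain intensity depending on which is worse".

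For GPC, SAP 27.2 says: "Global perceived change is an ordered categorical variable with repeated measurements and will be analyzed using a GLMM". It lists no model terms. By contrast, SAP 27.1 names baseline leg pain, age and gender for the primary model, and 27.2 reuses that model for back pain, disability and bothersomeness.

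SAP section 15 schedules GPC at days 5 and 10. The timing table in that section also marks it at the end-of-study visit. There is no day-0 assessment, and for a rating of change there could not be one. Leg and back pain are both recorded at day 0, and Protocol 6.5.1 takes baseline pain as the mean of two day-0 recordings.

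The added-covariate analyses in SAP 27.5 repeat only the primary analysis, so they do not reach GPC.

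**The concern.** The SAP already accepts that baseline pain can stand in as a covariate for an outcome other than pain itself. It does so even for opioid use, which section 15 records at day 0. GPC is a patient rating of the same sciatica problem, yet it falls outside both sentences of 27.3. Someone coding the analysis from the text would fit the ordinal model with no baseline term.

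What is at stake is the power and precision of one secondary comparison. There is also a matter of definition: in an ordinal logistic model, adding a prognostic covariate changes the odds ratio being estimated from marginal to conditional. The choice should therefore be made before treatment differences are seen.

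**Working it through.** **Step 1. What each outcome receives.**

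| Outcome | Day-0 value of the outcome | Covariate named in the SAP |
|---|---|---|
| Leg pain (primary) | yes | own baseline, age, gender (27.1) |
| Back pain, disability, bothersomeness | yes | as for the primary outcome (27.2) |
| Work/study | yes | own baseline (27.3, general rule) |
| Opioid use | yes | worse of baseline leg or back pain (27.3) |
| Rescue medication | no | worse of baseline leg or back pain (27.3) |
| 30% and 50% responders | no responder status at day 0, but leg pain is recorded | none in the 27.2 line |
| GPC | no | none |

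**Step 2. The plan's own figure.** SAP section 11 uses a "minimum difference of interest between the Naproxen group and the placebo group of 1.5 at day 10", "Assuming a standard deviation SD of 2.5", and "90% power and a two-tailed 5% significance level". Protocol 9.1 adds the test: "with a SD of 2.5 using a two-sample t test". SAP section 10 gives the ratio: "Allocation to Naproxen or placebo will be at a 1:1 ratio".

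- Normal approximation: n per arm = 2 × (1.960 + 1.282)² × 2.5² / 1.5² = 58.4, rounded up to 59.
- Exact t test: 60 per arm (power 90.3% at 60, 89.8% at 59).
- Loss allowance: 120 / 0.8 = 150.

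The stated 60 per arm and 150 in total are reproduced. They concern leg pain. The documents state no power for GPC, and nothing in this point changes these figures.

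**Step 3. Linear approximation.** Adjusting for a covariate with correlation r multiplies the residual variance by 1 − r². So 120 evaluable patients act like 120 / (1 − r²). Starting from an assumed 80% unadjusted power, adjusted power is Φ[(1.960 + 0.842) / √(1 − r²) − 1.960].

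| r (assumed) | 1 − r² | 120 patients act like | Power, from 80% |
|---|---|---|---|
| 0.1 | 0.99 | 121 | 80.4% |
| 0.2 | 0.96 | 125 | 81.6% |
| 0.3 | 0.91 | 132 | 83.6% |
| 0.4 | 0.84 | 143 | 86.4% |
| 0.5 | 0.75 | 160 | 89.9% |

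**Step 4. Simulation on the ordinal scale.** The inputs below are assumptions, because the documents give none of them except the category list:

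- 60 evaluable patients per arm;
- the eight response categories listed in SAP 26.1, with control-arm probabilities .03/.12/.20/.25/.25/.08/.05/.02;
- conditional odds ratio 2.5;
- day 10 only;
- proportional-odds model without and with the baseline covariate, 3000 trials per scenario.

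| r | Power without | Power with | Gain (points) | Median OR without / with | Type I error without / with |
|---|---|---|---|---|---|
| 0 | 81.2% | 81.2% | 0.0 | 2.55 / 2.56 | 4.9% / 5.0% |
| 0.1 | 79.7% | 79.8% | 0.1 | 2.49 / 2.52 | 4.5% / 4.6% |
| 0.2 | 77.8% | 79.7% | 1.9 | 2.46 / 2.54 | 4.9% / 5.3% |
| 0.3 | 74.8% | 79.8% | 5.0 | 2.40 / 2.53 | 5.0% / 5.3% |
| 0.5 | 65.4% | 78.9% | 13.5 | 2.17 / 2.56 | 5.1% / 6.0% |

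The conditional odds ratio is held at 2.5. Adjusted power therefore stays near 80%, while unadjusted power falls as the omitted covariate pulls the odds ratio towards 1. The Monte Carlo standard error is √(0.8 × 0.2 / 3000) = 0.7 points for power near 80% and √(0.05 × 0.95 / 3000) = 0.4 points for type I error. Both models were fitted to the same trials, so the differences are steadier than the single figures. The 6.0% at r = 0.5 lies (6.0 − 5.0) / 0.4 = 2.5 standard errors above 5%, so the gain in that row is somewhat flattered.

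The two methods agree closely up to r = 0.2 (1.6 and 1.9 points). At r = 0.3 they give 3.6 and 5.0 points.

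**The case against.** The strongest reply is that leaving a change rating unadjusted is a legitimate choice. The comparison is randomised, and unadjusted type I error was 4.5% to 5.1% in the simulation. The GPC question (Protocol 6.5.6) asks patients to compare now with then, so its correlation with baseline severity could be low. At r = 0.1 nothing is gained. The simulation also uses one time point, whereas the plan has repeated measurements. All of this stands. It limits the size of the point, but gives no reason against the adjustment: no power was lost at r = 0 or 0.1.

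A reader might infer more than the text supports, in two ways:

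- **That the SAP has decided on an unadjusted GPC analysis.** It has not said so. The rule in 27.3 does not address outcomes that lack a baseline, and the GPC line in 27.2 does not list even treatment or time. The SAP is silent on GPC covariates; it does not rule them out.
- **That GPC is the only outcome in this position.** The responder line in 27.2 names no covariate either, and responder status does not exist at day 0. Baseline leg pain enters the responder definition, but that is not the same as being a model term.

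A further fair objection is that changing GPC alone would leave the secondary models uneven. That is why the responder models belong in the same edit.

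**Conclusion.** The point holds as a small, nearly free gain in precision for a secondary outcome. Read as written, SAP 27.3 and 27.2 give GPC no baseline term, while a collected covariate that the SAP already uses as a substitute is left out.

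The gain is about 0, 2 and 5 percentage points of power at r = 0.1, 0.2 and 0.3. These figures rest on the assumed r, category probabilities, odds ratio of 2.5 and 60 evaluable patients per arm. No document shows that baseline pain predicts GPC, so the lower end of the range is quite possible. No gain was calculated for age and gender or for the responder models.

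It would be wrong to conclude that the GPC test is biased or invalid. The primary analysis, its type I error and the sample size of 150 are untouched.

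**What to change.** Before unblinding, and preferably before data split by the A/B codes of SAP 33.2 are examined, amend SAP 27.3 as follows:

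1. Extend the second sentence to GPC, so that its ordinal model is also adjusted for baseline leg or back pain, whichever is worse.
2. State that the GPC odds ratio is then conditional on that covariate.
3. Apply the same principle to the 30% and 50% responder models by adjusting them for baseline leg pain.
4. Optionally add age and gender to these models, for consistency with 27.1.

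The cost is a sentence or two in the SAP. No new data, visits or patients are needed. The one consequence to accept is that the odds ratios become conditional. The SAP should therefore also say how any percentage difference, including the one behind the number needed to treat in 27.2, is obtained: from crude proportions or by averaging model predictions over the covariates.

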27.1 Analysis of the primary outcome

The primary objective of the NIS trial is to estimate and test treatment differences in leg pain intensity at 10 days after commencement of Naproxen or placebo. Multiple measurements taken on the same patient will be correlated. This is accounted for in the analysis by a mixed effects model; either a linear mixed model (LMM) or a generalized linear mixed model (GLMM) depending on the distribution of the leg pain intensity. The model includes fixed effects for treatment, time (11 time points), the treatment-by-time interaction, and baseline measurements of leg pain plus age and gender. The primary result will be the treatment effect estimates over the period of treatment with 95% CI.

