27.5 Sensitivity analyses

We intend to assess the robustness of the results by

- Repeating the primary analysis in the PPP.
- Analyze the primary outcome using multiple imputation (MI) (see 28.3).
- Repeating the primary ITT analysis by including each of the following baseline variables as a covariate:
 - o study centre (the stratification variable)
 - o previous NSAID use (yes/no)
 - o imaging findings

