33.2 Statistical Master File

After database lock the clinical datasets will be delivered to the sponsor specified as SPSS files, one file per form as specified in the data handling plan. The data will be analyzed blinded to the randomization codes. Each participant will be provided with a code A or B. When the analyses of the data are complete the investigators will be provided with which treatment (Naproxen or placebo) code A and B represents.

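### Allocation is blocked within centre but the main linear models leave centre out, so their standard errors may be slightly too large (minor)

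*SAP*

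**What the plan says.** SAP section 10 specifies 1:1 block randomisation stratified by centre, and Protocol 4.6 also stratifies by centre. Protocol 9.2.1 describes allocation as simple and unrestricted, then says in the next sentence that stratification by centre is done with blocks.

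The leg pain model in SAP 27.1 has fixed effects for treatment and time, "the treatment-by-time interaction, and baseline measurements of leg pain plus age and gender". Centre is not among them. The model may be "either a linear mixed model (LMM) or a generalized linear mixed model (GLMM) depending on the distribution of the leg pain intensity". SAP 27.2 uses the same model for back pain, RMDQ-S and SBI. Rescue medication and opioid use "will be analyzed using a suitable regression".

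SAP 27.3 explains the omission: "Study center (stratification variable) will not be included as covariate as we expect the majority of participants to be included at one center (Østfold". It adds "We will perform a sensitivity analysis with and without adjusting for center", and SAP 27.5 lists "study centre (the stratification variable" among the covariates to be added when the primary ITT analysis is repeated. SAP 27.3 closes the topic with "Provided that a sufficient number of patients are included from at least 4 centers, these can be treated as additional random effects". The protocol synopsis lists four centres.

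**The concern.** The analysis does not follow the design. With blocks, the arms are nearly balanced within each centre, so differences between centres largely cancel out of the treatment comparison. A linear model that omits centre leaves those differences in its residual variance and so overstates the standard error. The expectation of one dominant centre is a reason why the loss is small, not a reason to omit the factor.

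Two wordings add to the problem. The random-effect sentence does not say whether it concerns the main or the sensitivity model, does not say how many patients are enough, and is phrased as an option. With four centres it would estimate a variance from four levels. The wording of Protocol 9.2.1 also matters here, because under truly unrestricted allocation the standard error without centre would be valid.

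At stake is a little precision in the primary interval and one model choice left open.

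**Working it through.** **Inputs from the documents.** Difference 1.5, SD 2.5, two-sided 5%, 90% power, 60 per arm, 150 in total (Protocol 9.1, SAP 11); four centres (synopsis).

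**Assumed, because the documents do not give them.** The share of residual variance lying between centres (ICC), the split of patients over centres, and blocks of 4.

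**1. The plan's own figure.** The normal approximation gives 2 × (1.960 + 1.282)² × 2.5² / 1.5² = 58.4, so 59 per arm. Exact t-test power is 89.8% at 59 and 90.3% at 60, so 60 per arm reproduces. 120 / 0.80 = 150.

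**2. Excess in the reported standard error.** With centre shares p_k:

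- h = 1 − Σp_k²
- v = ICC·h / (ICC·h + 1 − ICC), the expected share of the variance in the trial that lies between centres
- SE excess = 1/√(1 − v) − 1

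Example, 70/10/10/10 at ICC 0.10: h = 1 − (0.49 + 3 × 0.01) = 0.48; v = 0.048 / 0.948 = 0.0506; 1/√0.9494 = 1.026, so 2.6%. For 85/5/5/5, h = 0.27; for four equal centres, h = 0.75.

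**3. Type I error and power.** These were simulated with t tests on 118 df (no centre) and 115 df (centre as a fixed effect), N = 120, 70/10/10/10, 100,000 trials per cell.

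| ICC | 0 | 0.02 | 0.05 | 0.10 | 0.20 |
|---|---|---|---|---|---|
| SE excess, 85/5/5/5 (%) | 0 | 0.3 | 0.7 | 1.5 | 3.3 |
| SE excess, 70/10/10/10 (%) | 0 | 0.5 | 1.3 | 2.6 | 5.8 |
| SE excess, four equal centres (%) | 0 | 0.8 | 2.0 | 4.1 | 9.0 |
| Type I error without centre (%) | 4.9 | 4.9 | 4.8 | 4.5 | 4.0 |
| Power without centre (%) | 90.2 | 90.3 | 90.4 | 90.8 | 91.4 |
| Power with centre (%) | 90.2 | 90.4 | 90.8 | 91.7 | 93.3 |

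With centre in the model, type I error is 5.0% throughout. Under unrestricted allocation at ICC 0.10, type I error without centre is also 5.0%, so the conservatism comes from the blocking.

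**4. The same effect in points on the pain scale.** Suppose the largest centre holds a share p of patients and differs from the rest by d points. The centre share of variance is then p(1 − p)d² / 2.5². With p = 0.60 and d = 1.0, this is 0.24 / 6.25 = 3.8%, and 1/√(1 − 0.0384) = 1.020. Simulation (72/24/12/12) gave a mean reported SE of 0.456 against a true SD of 0.446. With p = 0.85 and d = 1.0, the share is 0.1275 / 6.25 = 2.0% and the excess 1.0%.

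**5. A model closer to the plan.** This was a random-intercept model over 10 days with complete data, assumed baseline correlation 0.5 and within-patient correlation 0.7, at 70/10/10/10. The SE of the day-10 difference without and with centre was 0.396 and 0.391 at ICC 0.05, 0.397 and 0.386 at 0.10, and 0.395 and 0.375 at 0.20. Power went from 96.6 to 96.8%, 96.9 to 97.3%, and 97.5 to 98.2%. The SE ratios carry over; the power gain is smaller than with the t test.

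**6. Cost of adding centre.** Three degrees of freedom move the critical t from 1.9803 to 1.9808, or 0.03%.

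**7. The random-effect option.** With 105/15/15/15 patients, the centre variance is estimated as zero in 61, 43, 29, 17 and 7% of trials at ICC 0, 0.02, 0.05, 0.10 and 0.20.

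**The case against.** The SAP names centre as the stratification variable, gives a reason for leaving it out, and commits to results with and without it. For the primary outcome both will be reported, so the change mostly swaps their labels. The omission biases nothing and can only make the test cautious. Every size rests on an assumed ICC. Nothing in the documents supports 0.20, and four equal centres contradict the SAP's expectation of one dominant site. All of this stands, and it is why the point is minor and why the 85/5/5/5 and 70/10/10/10 rows should be read first. It does not justify the omission: a sensitivity analysis leaves the primary interval as it is, and SAP 27.5 lists the centre-adjusted repeat for the primary ITT analysis only.

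Another objection is that including centre only in linear models ties the covariate set to a model chosen from the data. That is true, but SAP 27.1 already leaves the choice of model open. The restriction has a sound reason: in logistic, ordinal or multinomial models, adding centre also changes the conditional odds ratio being estimated.

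Finally, a random-effect variance estimated as zero simply returns the model without centre, so the zero shares show no harm in themselves. This is correct. The case against that sentence is its vagueness and how little four levels can support. On Protocol 9.2.1, the other passages agree on blocking by centre, so the conflict is probably one of wording. It still needs settling, because the argument depends on it.

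**Conclusion.** The point holds and is minor. Allocation blocked by centre calls for centre in the main linear models, and the SAP's reason for leaving it out only limits the loss. With one dominant centre and an ICC of 0.02 to 0.10, the reported standard error is about 0.3 to 2.6% too large. In the t-test simulation at 70/10/10/10, adding centre then raises power by 0.1 to 0.9 percentage points. If centre does not predict outcome after baseline, age and gender, nothing is lost either way. The treatment estimate is unbiased, type I error is not inflated and N stays at 150. The direction rests on blocked allocation; the size rests on the assumed ICC, centre split and block size.

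**What to change.** - **Main models (SAP 27.1 to 27.3).** Include centre as a fixed effect in the linear models for leg pain, back pain, RMDQ-S and SBI, and make the model without centre the sensitivity analysis.
- **Pooling rule.** State a number. For example, centres with fewer than 10 randomised patients form one stratum, or join the next smallest centre if there is only one. With 135/5/5/5 patients and ICC 0.10, merging the three small centres cuts the SE excess from 1.0% (no centre) to 0.4%.
- **Timing.** Fix the rule before database lock and before any A/B-coded analysis. SAP 33.2 says "When the analyses of the data are complete the investigators will be provided with which treatment" each code stands for, so a deadline of unblinding would come after the comparisons had been seen.
- **Random effect.** Delete that sentence.
- **Other models.** If leg pain is analysed by a non-linear GLMM, and for the logistic, ordinal and multinomial outcomes, keep centre adjustment as a sensitivity analysis. For rescue medication and opioid use, include centre only if the regression chosen is linear.
- **Protocol 9.2.1.** Reconcile the unrestricted and the blocked descriptions of allocation.

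The cost is two or three SAP sentences, a one-line pooling rule, one clarified protocol sentence and about 3 degrees of freedom. Sample size and data collection do not change.
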